#### 9.3.2 Exclusion Criteria

Subjects with any of the following criteria will be excluded from this study:

- 1. Other malignancy active within the previous 2 years except for basal or squamous cell skin cancer, superficial bladder cancer, or carcinoma in situ of the cervix or breast that has completed curative therapy.
- 2. Subjects with any active autoimmune disease (Appendix 5) or a documented history of autoimmune disease, except for subjects with vitiligo or resolved childhood asthma/atopy.
- 3. Known human immunodeficiency virus (HIV) infection.
- 4. Active infection requiring therapy, including known positive tests for Hepatitis B surface antigen or Hepatitis C ribonucleic acid (RNA).
- 5. Major surgery within 4 weeks before the first dose of study drug.
- 6. Concurrent medical condition requiring the use of immunosuppressive medications or immunosuppressive doses of systemic medications, such as steroids or absorbed topical steroids (doses >10 mg/day prednisone or equivalent).
- 7. Brain metastases that are untreated or in the posterior fossa or involve the meninges. Subjects with stable or progressing brain metastases (except in the posterior fossa or involving the meninges) previously treated with brain stereotactic radiotherapy (SRT), whole-brain radiotherapy (WBRT) and/or surgery are allowed as long as the subject is asymptomatic neurologically and does not require immediate local intervention (radiotherapy and/or surgery). In addition, subjects must be off immunosuppressive doses of systemic steroids (>10 mg/day prednisone or equivalent) for at least 4 weeks before study drug administration.
- 8. Prolongation of corrected QT (QTcF) interval to >450 msec for males and females, when electrolytes balance is normal.

Eisai Confidential Page 62 of 138

- 9. Significant cardiovascular impairment: history of congestive heart failure greater than New York Heart Association (NYHA) Class II, uncontrolled arterial hypertension, unstable angina, myocardial infarction, or stroke within 6 months of the first dose of study drug, or cardiac arrhythmia requiring medical treatment (including oral anticoagulation).
- 10. Subjects on oral anticoagulants including low dose aspirin. To meet eligibility, these subjects can be switched to receive preventive dose of low molecular weight heparin (LMWH). It is recommended that their LMWH treatment is stopped 24 hours before the intratumoral injection and resumed again 24 hours after the injection.
- 11. Any history of a medical condition or a concomitant medical condition that, in the opinion of the investigator, would compromise the subject's ability to safely complete the study.
- 12. Females who are breastfeeding or pregnant at Screening or Baseline (as documented by a positive beta-human chorionic gonadotropin [β-hCG] (or human chorionic gonadotropin [hCG]) test with a minimum sensitivity of 25 IU/L or equivalent units of β-hCG [or hCG]). A separate baseline assessment is required if a negative screening pregnancy test was obtained more than 72 hours before the first dose of study drug.
- 13. Females of childbearing potential must not have had unprotected sexual intercourse within 30 days before study entry and must agree to use a highly effective method of contraception (total abstinence [if it is their preferred and usual lifestyle], a contraceptive implant, an oral contraceptive, or have a vasectomized partner with confirmed azoospermia) throughout the entire study period and for 180 days after study drug discontinuation. For sites outside of the EU, it is permissible that if a highly effective method of contraception is not appropriate or acceptable to the subject, then the subject must agree to use a medically acceptable method of contraception, ie, double barrier methods of contraception such as condom plus diaphragm or cervical/vault cap with spermicide. If currently abstinent, the subject must agree to use a highly effective method as described above if she becomes sexually active during the study period or for 180 days after study drug discontinuation. Females who are using hormonal contraceptives must have been on a stable dose of the same hormonal contraceptive product for at least 28 days before dosing and must continue to use the same contraceptive during the study and for 180 days after study drug discontinuation.
- 14. Male subjects who are partners of women of childbearing potential must use a condom and spermicide and their female partners if of childbearing potential must use a highly effective method of contraception (see methods described above in Exclusion Criterion #13) beginning at least 1 menstrual cycle prior to starting study drug(s), throughout the entire study period, and for 180 days after the last dose of study drug, unless the male subjects are totally sexually abstinent or have undergone a successful vasectomy with confirmed azoospermia or unless the female partners have been sterilized surgically or are otherwise proven sterile. No sperm donation is allowed during the study period or for 180 days after study drug discontinuation.

Eisai Confidential Page 63 of 138

- Known hypersensitivity to E7766 or any of the excipients or prior therapy with E7766 or any other STING agonist.
- 16. Use of illegal recreational drugs.
- 17. Currently enrolled in another clinical study or used any investigational drug or device within 28 days preceding informed consent.

## 9.3.3 Removal of Subjects from Therapy or Assessment

The investigator may withdraw the subject from the study at any time for safety or administrative reasons. The subject may stop study drug or withdraw from the study at any time for any reason.

The investigator may discontinue treating a subject with study treatment or withdraw the subject from the study at any time for safety or administrative reasons. The subject may decide to discontinue study treatment or withdraw from the study at any time for any reason. The reason for discontinuation will be documented. If a subject discontinues study treatment, the subject will enter the Follow-Up Period and complete protocol-specified off-treatment visits, procedures, and survival follow-up unless the subject withdraws consent. The investigator should confirm whether a subject will withdraw from study treatment but agree to continue protocol-specified, off-treatment study visits, procedures, and survival follow-up, or whether the subject will withdraw consent. If a subject withdraws consent, the date will be documented in the source documents.

During the Follow-Up Period, subjects who have discontinued study treatment without progression should have disease assessments every 6 weeks in case of solid tumors and 12 weeks in case of lymphomas from the date of the last assessment until disease progression is documented or another anticancer therapy is initiated.

All subjects will be followed for survival every 12 weeks for up to 2 years, except where a subject withdraws consent or the sponsors choose to halt survival follow-up after completion of the primary study analysis.

[figure not shown]
#### 9.4 Treatments

#### 9.4.1 Treatments Administered

Subjects enrolled in the study will receive E7766 administered intratumorally.

Eisai Confidential Page 64 of 138

#### 9.4.1.1 Dosing Schedules

E7766

A fully equipped and functional crash cart must be available in the unit where a subject is to be administered E7766.

E7766 will be administered in 3-week cycles, with treatment as follows:

- Induction (Cycle 1): Days 1, 8, 15
- Maintenance (Cycle 2 and after): on Day 1 of each cycle, Q3W.

In the Maintenance treatment portion, ie, Cycle 2 forward, if a scheduled dosing is missed or delayed, this dosing will be administered as soon as allowed under dose interruption/retreatment guidelines. Treatment cycles will be synchronized to the new dosing day, ie, the day of administration of the made-up dosing will be considered Day 1 of the next cycle. This synchronization will include all cycle Day 1 assessments and procedures, but will exclude response assessments as outlined in Section 9.5.1.3.

Eisai Confidential Page 65 of 138

## 9.4.1.2 Dose Adjustments

### E7766 Dose Adjustments

In the Dose Escalation part, dose adjustments may be allowed at the discretion of the investigator after discussion with the sponsors. Subject may be allowed to continue study drug at a reduced dose, if this is judged to be in their best interest. E7766 dose reductions and interruptions should be carried out as outlined in Table 4.

## Guidelines for dose adjustments after Cycle 1

E7766 dose reduction and interruption for subjects who experience therapy-related toxicity (as assessed by the investigator) will be in accordance with the dose modification guidelines described in Table 4.

• Subjects who experience toxicities that could have been qualified as DLTs may, at the discretion of the investigator and after discussion with the sponsors, be allowed to continue study drug at a reduced dose according to these dose modification guidelines, if this is judged to be in their best interest.

For subjects who require dose interruption due to E7766-related toxicity in Cycle 2 or beyond, the treatment may re-start once the toxicity has been resolved to Grade  $\leq 1$  or baseline according to the dose reduction and interruption instructions in Table 4.

Table 4 E7766 Dose Reduction and Interruption Instructions

E7766-Related Toxicity a	During Therapy	Approximate Dose Adjustment		
Grade 1				
	Continue E7766 treatment.			
All occurrences	If CRS, then interrupt E7766	Maintain dose level.		
	until Grade 0.			
	Grade 2 b			
	Interrupt E7766 until resolved to			
1st occurrence	Grade ≤1 or baseline.	Maintain dose level.		
1st occurrence	If CRS, then interrupt E7766	If CRS, consider dose reduction.		
	until Grade 0°.			
	Interrupt E7766 until resolved to	Consider reduction by 1 dose level of starting		
2nd occurrence	Grade ≤1 or baseline.	dose, if dose delayed.		
(same toxicity)	If CRS, then interrupt E7766	If CRS, then consider further dose reduction.		
	until Grade 0°.			
3rd occurrence	Interrupt E7766 until resolved to	Reduce by 1 or 2 dose levels of starting dose,		
	Grade $\leq 1$ or baseline c .			
(same toxicity)	If CRS, then discontinue E7766.	if appropriate.		
4th occurrence	Interrupt E7766 until resolved to	Digayag with anangara		
(same toxicity)	Grade $\leq 1$ or baseline c .	Discuss with sponsors.		
Grade 3 b				
1st occurrence	Interrupt E7766 until resolved to	Reduce by 1 dose level of starting dose		
	Grade $\leq 1$ or baseline c .			
	If CRS, then discontinue E7766.			

Eisai Confidential Page 66 of 138

2nd occurrence	Interrupt E7766 until resolved to	Padvas by 2 dags levels of starting dags	
(same toxicity)	Grade $\leq 1$ or baseline c .	Reduce by 2 dose levels of starting dose	
3rd occurrence	Discontinue E7766 treatment	Not applicable	
(same toxicity)			
Grade 4 d : Discontinue E7766			

For grading, see Common Terminology Criteria for Adverse Events (CTCAE v. 5.0)

- a: Excluding alopecia, anemia, lymphocytopenia, and asymptomatic neutropenia. Initiate optimal medical management for nausea, vomiting, diarrhea, and/or fever before any E7766 interruption or dose reduction. b: Applicable only to those Grade 2 toxicities judged by the subject and physician to be intolerable and to all Grade 3 toxicities.
- c: Interruption of E7766 treatment for more than 21 days (due to E7766-related toxicities) will require a discussion with the sponsors before treatment can be resumed.
- d: Excluding laboratory abnormalities judged to be non-life-threatening, in which case manage as Grade 3.

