**E7766 Dose Reduction and Interruption Instructions** 

E7766-Related Toxicity a	During Therapy	Approximate Dose Adjustment		
•	Grade 1			
All occurrences	Continue E7766 treatment. If CRS, then interrupt E7766 until Grade 0.	Maintain dose level.		
Grade 2 b				
1st occurrence	Interrupt E7766 until resolved to Grade ≤1 or baseline. If CRS, then interrupt E7766 until Grade 0°.	Maintain dose level. If CRS, consider dose reduction.		
2nd occurrence (same toxicity)	Interrupt E7766 until resolved to Grade ≤1 or baseline. If CRS, then interrupt E7766 until Grade 0°.	Consider reduction by 1 dose level of starting dose, if dose delayed.  If CRS, then consider further dose reduction		
3rd occurrence (same toxicity)	Interrupt E7766 until resolved to Grade ≤1 or baseline c .  If CRS, then discontinue E7766.	Reduce by 1 or 2 dose levels of starting dose if appropriate.		
4th occurrence (same toxicity)	Interrupt E7766 until resolved to Grade ≤1 or baseline c .	Discuss with sponsors.		
	Grade 3 b			
1st occurrence	Interrupt E7766 until resolved to Grade ≤1 or baseline c .  If CRS, then discontinue E7766.	Reduce by 1 dose level of starting dose		
2nd occurrence (same toxicity)	Interrupt E7766 until resolved to Grade ≤1 or baseline c .	Reduce by 2 dose levels of starting dose		
3rd occurrence	Discontinue E7766 treatment.	Not applicable		

CRS = cytokine release storm.

For grading, see Common Terminology Criteria for Adverse Events (CTCAE v. 5.0)

Eisai Confidential Page 17 of 138

- a: Excluding alopecia, anemia, lymphocytopenia, and asymptomatic neutropenia. Initiate optimal medical management for nausea, vomiting, diarrhea, and/or fever before any E7766 interruption or dose reduction. b: Applicable only to those Grade 2 toxicities judged by the subject and physician to be intolerable and to all Grade 3 toxicities.
- c: Interruption of E7766 treatment for more than 21 days (due to E7766-related toxicities) will require a discussion with the sponsors before treatment can be resumed.
- d: Excluding laboratory abnormalities judged to be non-life-threatening, in which case manage as Grade 3.

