### Management of Cytokine Release Storm

Cytokine release storm (CRS) has been identified as a potential safety risk in immunotherapies, especially drugs that act as agonists for immune activation. A full guidance for identification and management of CRS is provided in the "Management of Cytokine Release Storm and Organ Toxicity" table below. IL-6 levels will be assessed by the site as clinically indicated. For E7766 dose adjustments and interruptions for the management of CRS, refer to "E7766 Dose Reduction and Interruption Instructions." table.

CRS Grade (CTCAE)	Sign/Symptom	Management
Grade 1	Fever or	Acetaminophen and hypothermia blanket as needed for fever
	Grade 1	• Ibuprofen if fever is not controlled with above; use with caution
	organ toxicity	or avoid if thrombocytopenic
		
 
Assess for infection with blood and urine cultures, and chest x-ray
 

		• Consider antibiotics and filgrastim (if neutropenic)
		IV fluids as needed
		
 
Symptomatic management of constitutional symptoms and organ toxicities
 

		• Consider IL-6 antagonist  for persistent (greater than 3 days) o
~		refractory fever
Grade 2	Hypotension	• IV fluid bolus of 500 – 1,000 mL normal saline; repeat as necessary to maintain SBP greater than 90 mmHg
		• Consider IL-6 antagonist  for hypotension refractory to fluid boluses
		• If hypotension persists after two fluid boluses and IL-6
		antagonist  , start vasopressors, transfer patient to ICU, and obtain ECHO
		• In patients at high-risk for severe CRS  , if hypotension persists
		after IL-6 antagonist  , if there are signs of hypoperfusion  or if
		there is rapid deterioration in the opinion of the clinician, may use dexamethasone 10 mg IV every 6 hours
		
 
Manage fever and constitutional symptoms as in Grade 1 CRS
 

	Hypoxia	Use supplemental oxygen as needed
		• Use IL-6 antagonist  with or without corticosteroids as in
		hypotension
		
 
Manage fever and constitutional symptoms as in Grade 1 CRS
 

	Grade 2	Manage organ toxicity as per standard guidelines
	organ toxicity	• Use IL-6 antagonist  with or without corticosteroids as in
		hypotension

Eisai Confidential Page 18 of 138

		Manage fever and constitutional symptoms as in Grade 1 CRS

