#### Risk Benefit assessment

In the current study, E7766 is being evaluated for the treatment of solid tumors or lymphomas, that are advanced, nonresectable, or recurrent and progressing since last antitumor therapy, and for which no alternative standard therapy exists. E7766 is a new agent with a novel mechanism of action and has demonstrated a potent and long lasting antitumor activity in nonclinical tumor models with nonsevere toxicity through intratumoral administration. Based on the antitumor activity of E7766 observed in nonclinical tumor models, E7766 is expected to demonstrate clinical activity and response in these subjects, for whom no alternative standard therapy exists and the prognosis is poor.

Eisai Confidential Page 47 of 138

Nonclinical safety assessments were conducted in mice and cynomolgus monkeys and they showed adverse effects consistent with the pharmacologic activity. Based on these studies, the following adverse effects may be anticipated in the FIH study:

- Systemic inflammation, manifested as described in the next 2 bullets below
- Cytokine elevation, including of IL-6, IP-10, MCP-1, IFNβ, and TNF-α, peaking at approximately 8 hours postdose, and which is likely to be markedly lower after 24 hours. The amplitude of cytokine response is not expected to change significantly upon repeated dosing.
- Local injection site irritation including reddening, swelling, and ulceration.
- Gastrointestinal signs, including diarrhea

Overall, considering the promising antitumor activity and limited toxicity of E7766 in nonclinical studies at the doses showing antitumor activity when administered via the intratumoral route, clinical evaluation of E7766 via the intratumoral route is planned in subjects with advanced solid tumors and lymphomas.

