#### 9.1.3.3 Extension Phase

In the Extension Phase, subjects who are receiving study drug at the end of the Treatment Phase will continue to receive drug treatment at the same dose and according to the Dosing Schedule described in Section 9.4.1.1.

In the **Treatment** and **Extension phases**, subjects will undergo disease assessments every 6 weeks in the case of solid tumors and 12 weeks in the case of lymphomas, and will discontinue study drug at the time of confirmed disease progression (per iRECIST or LYRIC), disappearance or nonavailability of any injectable lesions, development of unacceptable toxicity, subject request, withdrawal of consent, termination of the study program, pregnancy, or investigator decision.

An off-treatment assessment should occur within 30 days after the final dose of study treatment.

Subjects who are continuing to derive clinical benefit in the view of the investigator at the time of study termination by the sponsor, can continue to be treated with E7766 after discussion with the sponsors.

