### 9.4.1.4 Management of Cytokine Release Storm

Cytokine release storm (CRS) has been identified as a potential safety risk in immunotherapies, especially drugs that act as agonists for immune activation. Guidance for identification and management is provided in Table 5. IL-6 will be assessed by the site as clinically indicated. For E7766 dose adjustments and interruptions for the management of CRS, refer to Table 4.

Table 5 Management of Cytokine Release Storm and Organ Toxicity

CRS Grade	Sign/Symptom	Management
(CTCAE)		
Grade 1	Fever or Grade 1 organ toxicity	
 
Acetaminophen and hypothermia blanket as needed for fever
 
Ibuprofen if fever is not controlled with above; use with caution or avoid if thrombocytopenic
 
Assess for infection with blood and urine cultures, and chest x-ray
 
Consider antibiotics and filgrastim (if neutropenic)
 
IV fluids as needed
 
Symptomatic management of constitutional symptoms and organ toxicities
 
Consider IL-6 antagonist for persistent (greater than 3 days) or refractory fever
 

Grade 2	Hypotension	
 
IV fluid bolus of 500 – 1,000 mL normal saline; repeat as necessary to maintain SBP greater than 90 mmHg
 
Consider IL-6 antagonist¹ for hypotension refractory to fluid boluses
 
If hypotension persists after two fluid boluses and IL-6 antagonist¹, start vasopressors, transfer patient to ICU, and obtain ECHO
 
In patients at high-risk for severe CRS², if hypotension persists after IL-6 antagonist¹, if there are signs of hypoperfusion³ or if there is rapid deterioration in the opinion of the clinician, may use dexamethasone 10 mg IV every 6 hours
 
Manage fever and constitutional symptoms as in Grade 1 CRS
 

	Hypoxia  Grade 2 organ toxicity	
 
Use supplemental oxygen as needed
 
Use IL-6 antagonist with or without corticosteroids as in hypotension
 
Manage fever and constitutional symptoms as in Grade 1 CRS
 
Manage organ toxicity as per standard guidelines
 
Use IL-6 antagonist with or without corticosteroids as in hypotension
 
Manage fever and constitutional symptoms as in Grade 1 CRS
 

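### Table 4 footnote b lets a third Grade 2 cytokine release storm escape the mandatory stop if the event is judged tolerable

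*Protocol*

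**What the plan says.** Protocol section 9.4.1.4 gives medical management of CRS in Table 5 and leaves dosing to the general table: "For E7766 dose adjustments and interruptions for the management of CRS, refer to Table 4". The synopsis has the same cross-reference to its own copy of that table.

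Table 4 (section 9.4.1.2, repeated in the synopsis) places CRS instructions inside the rows for each grade:

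- Grade 1, all occurrences: "Continue E7766 treatment. If CRS, then interrupt E7766 until Grade 0".
- Grade 2, first and second occurrence: interrupt until Grade 0, with dose reduction to be considered.
- Grade 2, third occurrence: "If CRS, then discontinue E7766".
- Grade 3, first occurrence: the same discontinuation instruction.

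Footnote b is attached to the Grade 2 and Grade 3 headings: "Applicable only to those Grade 2 toxicities judged by the subject and physician to be intolerable and to all Grade 3 toxicities". The Grade 1 row does not carry it. The synopsis copy of the footnote has the same wording. The SAP (section 5.6.1.3) refers to the protocol for dose modifications and adds no rule.

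**The concern.** The footnote exempts one class, Grade 3, from the intolerability test and does not name CRS. A tolerable Grade 2 CRS therefore carries a weaker written instruction than a Grade 1 CRS, which interrupts dosing every time.

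The clause that matters is the third-occurrence stop. It exists for the subject who reacts repeatedly, and the protocol gives reason to expect repetition. Its risk-benefit text says of the nonclinical findings: "The amplitude of cytokine response is not expected to change significantly upon repeated dosing". A Grade 2 event under Table 5 includes hypotension managed with fluid boluses. If the bolus works, subject and physician could reasonably call the event tolerable, and the stop would then not bind. Two sites could also count differently, because the table does not say whether a tolerable event adds to the tally towards the third. At stake is a safety stopping rule in a first-in-human study of this route of administration.

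**Working it through.** The plan states no figure to reproduce. The check is a trace of the rules, with a little arithmetic on timing.

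**Step 1. List the CRS clauses in Table 4 and see which fall under the intolerability test.**

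| Grade and occurrence | CRS instruction | Status | Conditional under footnote b? |
|---|---|---|---|
| 1, all | interrupt to Grade 0 | mandatory | no |
| 2, first | interrupt to Grade 0 | mandatory | yes |
| 2, first | consider reduction | optional | yes |
| 2, second | interrupt to Grade 0 | mandatory | yes |
| 2, second | consider further reduction | optional | yes |
| 2, third | discontinue | mandatory | yes |
| 2, fourth | none specific to CRS | – | – |
| 3, first | discontinue | mandatory | no |
| 3, second and third | none specific to CRS | – | – |

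That is 5 mandatory + 2 optional = 7 clauses. Of the 5 mandatory clauses, 1 + 1 + 1 = 3 become conditional: two interruptions and one discontinuation. Of the 2 CRS-specific stop clauses, 1 becomes conditional.

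**Step 2. Can the two conditional interruptions bind?** They matter only if the CRS is still Grade 2 when the next dose is due, because an event that has fallen to Grade 1 meets the unconditional Grade 1 rule. The schedule is "Induction (Cycle 1): Days 1, 8, 15", then Day 1 of each 3-week cycle, so doses fall on Days 1, 8, 15 and 22 and then every 21 days. Section 9.1.1.1 expects acute serious immune toxicity within hours to 3 days. Taking 3 days as the latest CRS onset, Grade 2 would have to last a further 7 − 3 = 4 days to reach the next dose up to Day 22, or 21 − 3 = 18 days in later maintenance. The risk-benefit text expects cytokines to peak at about 8 hours and to be markedly lower after 24 hours. These interruptions would rarely bind.

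**Step 3. Can the conditional stop bind?** Yes. One event after each of the Day 1, 8 and 15 injections gives a third event from Day 15 onwards, and the next injection is due on Day 22. The event need not persist until then; the stop depends on the count alone. If the third event is judged tolerable, footnote b removes the row that would end treatment.

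**Step 4. Look for a mandatory rule elsewhere.**

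- Section 9.1.3.3 allows discontinuation for "development of unacceptable toxicity, subject request, withdrawal of consent, termination of the study program, pregnancy, or investigator decision". For this case, that rests on judgement or on the subject's request.
- Section 9.1.1.2 lets a Grade 2 or other toxicity be designated a DLT, again by judgement and agreement.
- Section 9.1.1.2 lists a toxicity-related delay of 7 days or more in starting Cycle 2 as a DLT, and says treatment should stop if a DLT recurs at a lower dose. Neither rule reaches a tolerable Grade 2 CRS that causes no delay.
- The restart text in section 9.4.1.2 refers back to Table 4 and makes no CRS exception.
- Table 5 governs medical care only.

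Nothing restores the stop for the case in Step 3.

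**The case against.** The best reply is that the intent is plain. The CRS clauses read as event-specific overrides within general rows. Grade 1 CRS always interrupts and Grade 3 CRS stops treatment at once. The later rows (fourth Grade 2, second and third Grade 3) carry no CRS line, which makes sense only if such subjects are already off drug. For harm to follow, an investigator would have to treat Grade 2 CRS more leniently than Grade 1. The scenario also needs three separate Grade 2 events, with dose reduction offered for consideration after the first two. The SAP records that escalation ended early and that expansion will not enrol (sections 3.2.2 and 7), so a correction would reach few subjects.

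Most of this stands, and it limits the practical weight of the point. It does not supply the missing exception. The same evidence of intent shows that the footnote defeats the table it belongs to: a subject who continues after a tolerable third event meets a fourth-occurrence row with no CRS instruction.

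A reader might infer more from the count in Step 1, namely that three of five mandatory CRS protections are lost. The documents do not support that, since two of the three would almost never have operated (Step 2). Nor are subjects left unprotected: Table 5 care is unaffected, and treatment can still be stopped by judgement.

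**Conclusion.** The rule is wrong as written. Taken literally, the mandatory stop at the third Grade 2 CRS falls away when that event is judged tolerable, and the counting of tolerable events is undefined. The two interruptions share the defect in form but have little practical consequence.

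The conclusion rests on footnote b governing the whole block to which its marker is attached, and on the absence of any overriding CRS dosing rule in either document. It does not depend on a CRS rate.

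A reader might want to attach a percentage to the subjects who would escape the stop. None can be supported: the documents give no rate of Grade 2 CRS, no rate of tolerable judgements and no number of subjects with three events, and successive judgements by the same subject and physician would not be independent. The number is unknown and probably small. Nor should the point be read as affecting endpoints or analysis sets; Table 4 governs individual dosing.

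**What to change.** In footnote b, both in Table 4 and in the synopsis copy, add: *except CRS, for which the Grade 2 instructions apply to every event regardless of tolerability, and each event counts as an occurrence.* The first part restores the stop and the interruptions; the second settles the counting.

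The cost is one phrase in two places. No visits, procedures or subjects are added.
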